9.1.10.2.2 Surgical Procedure Guidelines

Routine general anesthesia according to institutional guidelines should be performed. Perioperative antibiotics and steroids are administered per institutional guidelines. Surgeons are encouraged to avoid the use of steroids where possible. Prohibited medications are detailed in Section 7.7 – Concomitant Therapy. Any permitted perioperative steroids should

be administered after all study related tissue and blood samples have been collected where possible.

Surgical procedures are tailored to the location of the tumor. The standard surgical procedures for this study are detailed in the Surgical Brochure. Importantly, surgical resection should be performed to margins identified at initial presentation as documented by the surgeon in Section 9.1.10.2.1. Also, the planned lymphadenectomy determined at initial presentation should be performed as documented by the surgeon in Section 9.1.10.2.1. In case of tumor progression, a more extensive procedure could be necessary in order to achieve negative resection margins. All study related biopsies should ideally be collected prior to resection being completed. The resection at each site should provide margins of at least 5 mm in the primary specimen, unless there are surgical contra-indications ie, proximity of great vessels. For the pembrolizumab treatment arm, the original surgical margins determined prior to initiation of pembrolizumab should be used to guide surgical resection. The choice of procedure as well as the choice of reconstruction, if deemed necessary, is at the discretion of the surgeon as per local SoC. The surgeon should describe in their operation report the extent of macroscopic disease with particular comparison to extent at initial presentation.

9.1.10.2.3 Post-operative Complications

Complications after major head and neck surgery encompass intraoperative and post-operative issues. Intraoperative issues may include hemostasis and tissue quality during dissections. Post-operative complications may be local and include bleeding, infection, or wound healing issues including pharyngeal fistulas, chylous fistulas, spinal accessory, hypoglossal and/or facial nerves, and other local, regional or free flap failure. These may contribute to increased length of inpatient hospital stay and time to initiation of post-operative RT ± cisplatin. In the absence of guidelines for the management of those, it will be to the discretion of the treating surgeon to manage these complications at the best of his/her knowledge as per local SoC.

9.1.10.2.3.1 Evaluation and Reporting of Post-operative Complications

Surgical complications will depend on the extent of the procedures, the site of intervention, and the technique of reconstruction. Given the variety of possible interventions a large variety of complications have to be foreseen. Potential post-operative complications include, but are not limited to:

Endoscopy:

- Dysphagia
- Odynophagia
- Voice changes and hoarseness
- Dyspnea
- Teeth damage

- Esophageal perforation
- Mediastinitis

Tumor Resection with or Without Reconstruction (Free or Regional/local Flap):	
• Hemorrhage/hematoma (requiring drainage, blood transfusion, or surgical intervention to stop bleeding)	• Loss of voice and hoarseness
• Epistaxis	• Partial or total flap loss
• G-tube complication	• Seroma
• Infection (including flap donor site and tracheostomy site)	• Spinal accessory nerve damage
• Fistula	• Hypoglossal nerve damage
• Wound healing complication	• Vagal nerve damage
• Dysphagia	• Facial nerve damage
• Odynophagia	• Phrenic nerve damage
• Tracheostomy complication	• Sympathetic trunk damage (Horner syndrome)
• Trismus	• Chyle leak

All post-operative complications will be reported and graded in the same way as other AEs (see Appendix 4) and will be identified by the investigator and/or surgeon as post-surgical complications. See Section 9.3.1 for reporting requirements for all AEs and SAEs considered to be post-surgical complications by the investigator.

9.1.10.2.4 Post-operative Care

Post-operative rehabilitation should proceed per institutional guidelines. These relate to tracheostomy status and resumption of oral diet. In general, all efforts should be made to de-cannulate participants with tracheostomies as fast as possible and start the participant on an oral diet. Sites are encouraged to get early involvement from speech and language pathologists, as per institutional guidelines, and to mobilize the participant as fast as his/her condition allows. These decisions need to be made by the treating head and neck surgeon and should be individualized to the participant's ability and needs.

9.1.10.2.5 Pathology Specimen

The resection specimen submitted to a local pathologist should include an entire surgically resected lesion with appropriate orientation and all resected lymph nodes (as well as tumor bed, if applicable), as per the guidelines provided in the Surgical Brochure and Pathology Manual. On pathologic exam, margins are defined as negative if ≥ 5 mm from the invasive front of tumor, close margin if between 1-5 mm, and positive margin if < 1 mm in the primary

resection specimen; an extranodal extension is defined as any extension of SCC from within a lymph node through the fibrous capsule and into the surrounding connective tissue. Surgeons may use margins from the tumor bed after resection and guidelines from the Surgical Brochure should be followed in this regard.

Neck dissection specimens should be processed per guidelines in the Vendor Manual but should include separation of the specimen into distinct neck levels prior to pathology submission.

Communication from surgeon to local pathologist should follow local practice and institutional guidelines. Sample transport, storage and shipment instructions for pathology specimens obtained during surgery will be provided in the Vendor Manual.

Representative specimens (slides) of tumor tissue collected during surgery from all participants will be submitted to the designated central laboratories (see Pathology Manual) for blinded pathological response assessment of the pCR and mPR endpoints, determination of high risk pathologic features (defined by evidence of positive margins or extranodal extension following surgical resection), and translational research (see Section 9.2.2).

9.1.11 Withdrawal/Discontinuation

Participants who discontinue study treatment prior to completion of the treatment period should be encouraged to continue to be followed for all remaining study visits.

When a participant withdraws from participation in the study, all applicable activities scheduled for the End of Study Visit should be performed at the time of withdrawal. Any AEs which are present at the time of discontinuation/withdrawal should be followed in accordance with the safety requirements outlined in Section 9.3 - Adverse Events, Serious Adverse Events and Other Reportable Safety Events.

Refer to Appendix 8 for Germany-specific guidance.

9.1.11.1 Withdrawal From Future Biomedical Research

Participants may withdraw their consent for Future Biomedical Research. Participants may withdraw consent at any time by contacting the principal investigator for the main trial. If medical records for the main trial are still available, the investigator will contact the Sponsor using the designated mailbox ([contact]). Subsequently, the participant's consent for Future Biomedical Research will be withdrawn. A letter will be sent from the Sponsor to the investigator confirming the withdrawal. It is the responsibility of the investigator to inform the participant of completion of withdrawal. Any analyses in progress at the time of request for withdrawal or already performed prior to the request being received by the Sponsor will continue to be used as part of the overall research trial data and results. No new analyses would be generated after the request is received.

In the event that the medical records for the main trial are no longer available (eg, if the investigator is no longer required by regulatory authorities to retain the main trial records) or the specimens have been completely anonymized, there will no longer be a link between the

participant's personal information and their specimens. In this situation, the request for specimen withdrawal cannot be processed.

9.1.12 Participant Blinding/Unblinding

This is an open label trial; there is no blinding for this trial.

9.1.13 Domiciling

Participants will be hospitalized for the protocol specified surgery and discharged as per local SoC.

At the discretion of the investigator, participants may report to the clinical research unit the evening prior to the schedule day of cisplatin administration and remain in the unit until 24 hours post-dose to ensure proper hydration. At the discretion of the investigator, participants may be requested to remain in the clinical research unit longer.

9.1.14 Calibration of Equipment

The investigator or qualified designee has the responsibility to ensure that any device or instrument used for a clinical evaluation/test during a clinical study that provides information about inclusion/exclusion criteria and/or safety or efficacy parameters shall be suitably calibrated and/or maintained to ensure that the data obtained is reliable and/or reproducible. Documentation of equipment calibration must be retained as source documentation at the study site.

9.2 Efficacy Assessments

9.2.1 Tumor Imaging and Assessment of Disease

The process for image collection and transmission to the central imaging vendor can be found in the SIM. Tumor imaging (head and neck, chest, and upper abdomen) is strongly preferred to be acquired by CT with contrast. Magnetic resonance imaging of the head and neck and upper abdomen should be used when CT with iodinated contrast is contraindicated or when mandated by local practice, or for imaging of the brain. The upper abdomen CT/MRI should cover the liver in its entirety. The choice between CT and MRI for the head and neck and upper abdomen imaging is left to the discretion of the investigator, but the same imaging technique, regarding modality and the use of contrast should be used in a participant throughout the study to optimize the visualization of existing and new tumor burden.

Participant eligibility will be determined using local assessment (investigator assessment) based on RECIST 1.1. All scheduled images for all study participants from the sites will be submitted to the central imaging vendor for BICR. In addition, images (including via other modalities) that are obtained at an unscheduled time point to determine disease progression, as well as imaging obtained for other reasons, but captures radiologic progression, should also be submitted to the central imaging vendor.

When the investigator identifies radiographic progression per RECIST 1.1, the central imaging vendor will perform expedited verification of radiologic progressive disease (PD) and communicate the results to the study site and Sponsor via email (see Section 9.2.1.4). Treatment should continue until PD/recurrence has been verified, initiation of a new anticancer treatment, pregnancy, death, withdrawal of consent, study conclusion or early termination, whichever occurs first (refer to Sec 8.1 – Discontinuation of Study Treatment).

9.2.1.1 Initial Tumor Imaging

Initial tumor imaging at Screening (contrast enhanced head and neck, chest, and upper abdomen CT scan or chest CT scan plus head and neck and abdomen MRI, and FDG-PET or FDG-PET/CT) must be performed within 28 days prior to the date of randomization. The site study team must review screening images to confirm the participant has evaluable disease per RECIST 1.1 prior to submitting to central imaging vendor.

The screening images must be submitted to the central imaging vendor for retrospective review.

Scans performed as part of routine clinical management are acceptable for use as screening tumor imaging if they are of diagnostic quality and performed within 28 days prior to the date of randomization and can be assessed by the central imaging vendor.

Fluorodeoxyglucose-positron emission tomography (FDG-PET or FDG-PET/CT) scans will only be performed at screening to help guide potential SoC neck dissections, if required. Diagnostic quality CT can be acquired on the PET/CT scanner while performing FDG-PET if that is the local standard practice (see procedure detail described in the SIM).

9.2.1.2 Tumor Imaging During the Study

The same modality (CT/MRI head and neck, chest, and upper abdomen) used at screening should be used during neoadjuvant and adjuvant treatment and during the post-treatment follow-up visits at the scheduled time points detailed in Section 2.0 – Schedule of Activities.

For participants in the pembrolizumab arm (Arm A), the first on-study imaging assessment should be performed after completion of 2 cycles of pembrolizumab treatment, at approximately Week 6 (\pm 10 days) from the date of randomization and before surgery. If the presurgery scan shows tumor flare this should not alter the timing or decision to proceed to surgery unless the tumor is unresectable. In the SoC arm (Arm B), the screening imaging will serve as the presurgery imaging. If the presurgery scans for Arm A or baseline scans for Arm B are done $>$ 14 days prior to the date of surgery, then repeat imaging prior to surgery will be required.

The first post-surgery imaging should be performed 12 weeks (\pm 7 days) after the end of RT \pm cisplatin. Subsequent tumor imaging should then be performed every 3 months (91 \pm 7 days), or more frequently if clinically indicated, until the end of Year 3 after randomization, then every 6 months (182 \pm 14 days) until the end of Year 5. For all post-surgery imaging, the clock will start at the end of RT \pm cisplatin (ie, last dose of). All of these visits should stay on track using the last dose of RT \pm cisplatin as the starting clock, ie,

if one of the imaging visits is late (even the first scan post-surgery), the participants will stay on the original schedule starting with the last dose of RT \pm cisplatin for all future visits; do not recalculate. Imaging timing should follow calendar days and should not be adjusted for delays in cycle starts. When the investigator identifies radiographic progression per RECIST 1.1, the site should submit the imaging with verification of progression (VOP) request to the central imaging vendor as soon as possible. Expedited VOP read will be performed by BICR and the results will be communicated to the site and Sponsor via email. If initial site-assessed PD was not verified by BICR, each subsequent imaging must be submitted to central imaging vendor with VOP request until PD has been verified. Treatment should continue until PD has been verified by BICR, initiation of a new anticancer treatment, pregnancy, death, withdrawal of consent, study conclusion or early termination, whichever occurs first. Of note, a participant will only discontinue from study treatment during the neoadjuvant phase if PD precludes surgery (refer to Sec 8.1 – Discontinuation of Study Treatment).

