- c The timeframe for surgery (after the presurgery visit) is 6 weeks (± 10 days) after randomization. Participants in Arm A are allowed to go to surgery outside of this timeframe if delays are due to an AE. Participants with delays other than for an AE may be considered with sponsor consultation.

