9.1.10 Treatment Administration

Study medication will be administered by the investigator and/or study staff according to the specifications within the Pharmacy Manual.

For the pembrolizumab arm (Arm A), presurgery neoadjuvant treatment (Treatment 1) should begin within 3 days of randomization. The timeframe for surgery (after the presurgery visit) is within 6 weeks (± 10 days) after randomization. Participants in Arm A are allowed to go to surgery outside of this timeframe if delays are due to an AE. Participants with delays other than for an AE may be considered with sponsor consultation. In the SoC arm (Arm B), following randomization participants will proceed directly to surgery as per local practice. In both treatment arms, post-surgery adjuvant treatment will start when participants have recovered adequately from the morbidity and/or complications from the surgery with RT \pm cisplatin starting at a recommended minimum range of within 6 weeks after surgery.

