9.10.2.1 Neoadjuvant Treatment (Treatment 1)

Only participants in Treatment Arm A/pembrolizumab will receive neoadjuvant pembrolizumab; participants in Treatment Arm A/pembrolizumab should proceed to surgery directly following the presurgery visit (within 6 weeks [\pm 10 days]) after randomization). Participants in Arm A are allowed to go to surgery outside this timeframe if delays are due to an AE. Participants with delays other than for an AE may be considered with sponsor consultation. Participants in the Treatment Arm B/SoC will proceed directly to surgery following within 4 weeks after randomization.

Visit timing requirements during the treatment period for Arm A are as follows:

- Assessments/procedures should be performed on Day 1 for each cycle.
- Pembrolizumab treatment cycles are 3 weeks (21 days).
- The window for each visit is \pm 3 days, unless otherwise noted. Cycle 1 treatment should begin within 3 days of randomization or as close as possible to that date on which the participant is allocated or assigned.

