9.10.2.2 Definitive Surgery

All participants will have presurgical assessments performed at Week 0-4 (\pm 10 days) for the SoC arm (Arm B) or Week 6 (\pm 10 days) for the pembrolizumab arm (Arm A), to allow assessment of disease status, PROs and safety monitoring. The window for this visit allows participants to proceed to surgery up to 10 days earlier or later if deemed necessary by the investigator.

Definitive surgery will be performed as per local SoC (Arm B/SoC) and following completion of neoadjuvant treatment (Arm A/pembrolizumab). Note: Participants in the pembrolizumab arm (Arm A) may proceed to surgery after 1 dose of pembrolizumab, if deemed appropriate, if the investigator has documented clinical evidence of tumor progression, preferably supported by radiographic evidence.

Participants who do not undergo surgery as originally planned may proceed directly to Treatment 2 and receive salvage RT plus cisplatin \pm pembrolizumab, depending on treatment assignment at the discretion of the investigator in consultation with the Sponsor.

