10.6.1.1 Event-Free Survival

The non-parametric Kaplan-Meier method will be used to estimate the EFS curve in each treatment group. The treatment difference in EFS will be assessed by the stratified log-rank test. A stratified Cox proportional hazard (PH) model with Efron's method of tie handling will be used to assess the magnitude of the treatment difference (ie, HR) between the treatment arms. The HR and its 95% CI from the stratified Cox model with Efron's method of tie handling and with a single treatment covariate will be reported. The stratification factors used for randomization (see Section 7.3) will be applied to both the stratified log-rank test and the stratified Cox model.

Since disease progression/recurrence is assessed periodically, disease progression/recurrence can occur any time in the time interval between the last assessment where the event was not documented and the assessment when the event is first documented. The true date of disease progression/recurrence will be approximated by the date of the first assessment at which the event is objectively documented. Death is always considered as an event. Participants who do not experience a disease progression/recurrence event will be censored at the last disease assessment. Sensitivity analyses will be performed for comparison of EFS based on investigator's assessment.

In order to evaluate the robustness of the EFS endpoint, 1 primary and 1 sensitivity analyses with a different set of censoring rules will be performed. The primary analysis follows the Intention-To-Treat principle. That is, PDs/ recurrences/deaths are counted as events regardless of missed study visits or initiation of new anticancer therapy. For the sensitivity analysis, if the events (disease progression, recurrence or death) are immediately after more than 1 missed disease assessment, the data are censored at the last disease assessment prior to missing visits. Also data after new anticancer therapy are censored at the last disease assessment prior to the initiation of new anticancer therapy. If a participant meets multiple criteria for censoring, the censoring criterion that occurs earliest will be applied. The censoring rules for primary and sensitivity analyses are summarized in [Table 13](#).

Table 13 Censoring Rules for Primary and Sensitivity Analyses of EFS

Situation	Primary Analysis	Sensitivity Analysis

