Disease progression, recurrence, or death documented after ≤ 1 missed disease assessment and before new anticancer therapy, if any	EFS event at date of documented disease progression, recurrence, or death	EFS event at date of documented disease progression, recurrence, or death
Disease progression, recurrent or death documented immediately after ≥ 2 consecutive missed disease assessments or after new anticancer therapy, if any	EFS event at date of documented disease progression, recurrence, or death	Censored at last disease assessment prior to the earlier date of ≥ 2 consecutive missed visits and new anticancer therapy, if any
No disease progression, no recurrence and no death; and new anticancer therapy is not initiated	Censored at last disease assessment	Censored at last disease assessment
No disease progression, no recurrence and no death; new anticancer therapy is initiated	Censored at last disease assessment	Censored at last disease assessment before new anticancer therapy
Abbreviations: EFS = event-free survival		

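### Post-surgery scans run from the end of radiotherapy, nominally 2 to 6 weeks later after randomisation in Arm A, and no public EFS sensitivity analysis tests the effect

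*Combined protocol and SAP*

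**What the plan says.** EFS is measured from randomisation (Section 10.4.1.1). Section 9.2.1.2 sets the scan calendar differently: "For all post-surgery imaging, the clock will start at the end of RT". The first scan is 12 weeks after the last dose, the next ones every 91 days, and late visits do not reset the schedule.

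Time to surgery differs by arm. For Arm A, footnote c of Section 2.1 says "The timeframe for surgery (after the presurgery visit) is 6 weeks" after randomisation, plus or minus 10 days. For Arm B, Section 9.10.2.1 says "Participants in the Treatment Arm B/SoC will proceed directly to surgery following within 4 weeks after randomization". Section 9.10.2.2 adds "All participants will have presurgical assessments performed at Week 0-4" with a 10-day window for Arm B, against week 6 for Arm A. After surgery the arms are treated alike: Section 9.1.10 has RT "starting at a recommended minimum range of within 6 weeks after surgery" in both.

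Section 10.6.1.1 states: "The true date of disease progression/recurrence will be approximated by the date of the first assessment at which the event is objectively documented". The comparison is a stratified log-rank test with a stratified Cox model. For robustness, "1 primary and 1 sensitivity analyses with a different set of censoring rules will be performed", together with an investigator-assessed version. The alternative rule in Table 13 ("Censored at last disease assessment prior to the earlier date of" two or more missed visits or new therapy) does not concern scan timing.

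**The concern.** If one arm is scanned later on the randomisation scale and progression takes the date of the scan, the same true progression can be recorded later in that arm. Log-rank and Cox would read this as benefit. Blinded central reading does not help, because the difference lies in the dates and not in the reading of the images. Both listed sensitivity analyses use the same scan dates.

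At stake is whether a small EFS advantage could be told apart from a scheduling effect. The plan as published has no analysis that would show this.

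**Working it through.** **1. Scan calendar.** Inputs: the surgery times above; RT start at 6 weeks after surgery (Sections 9.1.10 and 9.1.10.1.2); RT lasting 6 weeks (Section 9.1.10.1.2 gives 6 to 6.5); first scan 12 weeks after RT (Section 9.2.1.2).

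Week of first post-RT scan = surgery week + 6 + 6 + 12

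- Arm A: 6 + 6 + 6 + 12 = 30
- Arm B: 0 + 6 + 6 + 12 = 24, up to 4 + 6 + 6 + 12 = 28
- Nominal gap: 30 − 28 = 2 to 30 − 24 = 6 weeks

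Ten days is 1.43 weeks. With the windows, Arm A surgery falls at 4.57 to 7.43 weeks and Arm B at 0 to 5.43 weeks. The gap then runs from 4.57 − 5.43 = −0.86 to 7.43 − 0 = 7.43 weeks. It can narrow, widen or occasionally reverse.

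**2. What the gap does.** Take Arm B surgery at week 2: scans at weeks 26, 39, 52, against 30, 43, 56 in Arm A. In weeks 26 to 30 (4 weeks), progression is dated 39 in Arm B and 30 in Arm A, so 9 weeks earlier in Arm A. In weeks 30 to 39 (9 weeks), it is dated 39 and 43, so 4 weeks later in Arm A. With an even event rate these cancel on average: 9 × 4 − 4 × 9 = 0. Progression before week 26 has no such offset: unless picked up another way, it is dated 4 weeks later in Arm A. The residual effect therefore comes mainly from early progression and should tend to favour pembrolizumab.

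**3. Size.** The plan's alpha, event counts and control-arm curve are redacted, so there is no stated figure to reproduce. The simulation gave both arms the same true event times, with 357 per arm (714 / 2). Central assumptions:

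- cure model of the Appendix 9 form, 45% cured, latent median 10 months, half hazard before week 6
- RT starting 4 to 8 weeks after surgery and lasting 6 to 6.6 weeks
- pre-surgery scans in all of Arm A, and in Arm B when the baseline scan was more than 14 days before surgery
- 25% of events dated exactly
- 36-month accrual and 30-month minimum follow-up
- unstratified test at z = 1.96

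Runs gave 335 to 421 events, with Monte Carlo error of about 0.2 to 0.4 percentage points.

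| Scenario, no treatment effect | HR | One-sided error |
|---|---|---|
| Same scan clock in both arms | 1.00 | 2.3%–2.7% |
| Central | 0.976 | 4.0% |
| Fixed surgery gap of 2 / 4 / 6 weeks | 0.976 / 0.976 / 0.983 | 4.5% / 4.4% / 3.2% |
| Arm B surgery uniform over 0–5.4 weeks | 0.977 | 4.4% |
| No pre-surgery scans | 0.970 | 5.0% |
| 40% cured, latent median 8 months | 0.967 | 5.5% |
| 50% cured, latent median 12 months | 0.985 | 3.5% |
| 20% / 35% / 50% of events dated exactly | not listed | 4.7% / 3.4% / 3.1% |
| 6-week gap, hazard starting at week 18 | 0.997 | 2.5% |
| Interval-censored model, same data | 1.00 | 2.5%–2.7% |

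**4. Consistency check.** ln(0.976) = −0.0243, and SE(log HR) is about 2/√events. The shift in z is 0.0243 × √335 / 2 = 0.22 to 0.0243 × √421 / 2 = 0.25. Then Φ(−1.96 + 0.22) ≈ 4.1% and Φ(−1.96 + 0.25) ≈ 4.4%, in line with the simulated 4.0%.

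**5. Other models.** A large-sample simulation (1,000,000 per run) used exponential or cure-model EFS with medians of 18, 30 or 48 months, and gaps of 2, 4 and 6 weeks. The null HR was 0.925 to 1.012 with all events dated at scans and 0.967 to 1.015 with 60% so dated. With no gap it was 0.997 to 1.002. The effect does not grow steadily with the gap, because the 13-week grids interleave.

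**The case against.** The strongest reply is that the size is assumed. Event rates and alpha are redacted, and under some assumptions the effect disappears or slightly reverses. That stands, so the direction is likely but not certain. The effect is also small: 0.0243 is under a quarter of one standard error (0.10 to 0.11 with 335 to 421 events), so it matters only for a result near the boundary. That stands too.

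Surgery timing is not worded uniformly. Sections 5.1, 9.1.10 and 9.10.2.1 make 6 weeks an upper limit for Arm A, and Sections 5.1 and 9.1.10 leave Arm B to local practice. The 6-week end of the gap needs Arm B surgery on the day of randomisation. Even so, two 3-week cycles and a week-6 scan make about 6 weeks realistic for Arm A.

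Pre-surgery scans, unscheduled scans, biopsies and exactly dated deaths soften the effect. However, Sections 5.4.1.1.3 and 10.4.1.1 tie a neoadjuvant-phase event to progression that precludes surgery. The week-6 scan therefore offsets less than the central case credits, and the run without pre-surgery scans (0.970, 5.0%) may be closer.

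The SAP does acknowledge that progression falls between assessments, and the unseen supplemental SAP may hold more. The gap is shown only for the public text.

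The most substantive objection is that interval censoring does not correct a real shift in event times if recurrence risk runs from surgery. That case gave HR 0.95 and 7.2% error. It stands as a limit of the remedy.

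**Conclusion.** The concern holds as a modest potential bias in the primary endpoint. On the central assumptions it is about 2% in the hazard ratio (0.976), with one-sided error of 4.0% against an assumed 2.5%. The main scenarios span about 0.97 to 1.00 and 2.5% to 5.5%. The other survival models reach 0.925 at one extreme and 1.015 at the other. It most likely favours pembrolizumab. Matching the scan clocks removes it, which identifies the cause.

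The figures rest on assumed event rates, an assumed share of exactly dated events, an assumed 2.5% level and an unstratified test. This is a cheap improvement to the plan and does not call the primary analysis into question.

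**What to change.** - In Section 10.6.1.1 and Tables 13 and 14, pre-specify before unblinding a supportive stratified interval-censored proportional-hazards analysis of EFS in all three populations. Place progression or recurrence between the last negative and first positive central assessment, and keep deaths at their exact dates.
- Apply the planned pooling of small strata, since the three factors give 3 × 2 × 2 = 12 cells.
- Tabulate time from randomisation to surgery and to each scan by arm. This table is needed because the model cannot correct for risk that runs from surgery.
- Leave the stratified log-rank test as primary and the testing strategy unchanged.
- As a separate wording point, reconcile the follow-up column heading in Section 2.4, which counts three-monthly visits from the previous scan, with the imaging note in the same table, which rules out recalculating from earlier scans.

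The cost is SAP or supplemental SAP text and some programming on dates already collected, with no new visits and no alpha spent. The supportive estimate may come out slightly less favourable than the primary one.
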